5.3 Comparison of the 10g, 20g, and 40g LNS groups

If the dose by milk interaction is significant at the level of p < 0.1, we will use Tukey-Kramer's test for post-hoc pairwise comparisons between each intervention group in the one-factor ANOVA/ANCOVA described in section 5.1. The null-hypothesis of higher doses of LNS having no impact compared to lower doses will be rejected for each comparison that yields a Tukey-Kramer's adjusted p-value < 0.05.

If the dose by milk interaction is not significant at the level of p < 0.1 and if we conclude that LNS without milk is not inferior to milk-containing LNS, we will use Scheffe test in the one-factor ANOVA/ANCOVA described in section 5.1 to compare the mean scores among the combined 40g group (with and without milk), the combined 20g group (with and without milk), the 10g group, and the control group. The null-hypothesis of higher doses of LNS having no impact compared to lower doses will be rejected for each comparison that yields a Scheffe's adjusted p-value < 0.05.

If the dose by milk interaction is not significant at the level of p < 0.1 and if we do not conclude that LNS without milk is not inferior to milk-containing LNS, we will use Tukey-Kramer's test for post-hoc pairwise comparisons between each intervention group in the two-factor ANOVA/ANCOVA described in section 5.2. This model calculates the effect of dose while controlling for the effect of milk. The null-hypothesis of higher doses of LNS having no impact compared to lower doses will be rejected for each comparison that yields a Tukey-Kramer's adjusted p-value < 0.05.

5.4 Prevalence of severe and moderate to severe developmental delay The proportions of children demonstrating severe and moderate to severe developmental delays at age 18 months will be presented as shown in Table 3. We will use logistic regression, following the same approach outlined in sections 5.1 through 5.3. The results of pairwise comparisons will be indicated by superscripts. Relative risks and confidence intervals will be calculated based on the method described in Kleinman (2009).

6. General notes on statistical methods

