	6.1 Software
	6.2 Calculating z-scores
	6.3 Multiple comparisons
	6.4 Confidence intervals
	6.5 Interaction and effect modification
	6.6 Covariate adjustment
7.	References
8.	Tables
	Table 1 Comparison of developmental scores in the intervention groups at 18 months
	Table 2 Prevalence of developmental delay at 18 months of age 11

1. Study objectives

The main aim of the trial was to assess the safety and impact of supplementation with Lipidbased Nutrient Supplements (LNS) on linear growth of infants and young children and to identify individual, household, and village-level characteristics that modify the effects of LNS on child growth. A secondary aim is to similarly study the impact of LNS on various other (secondary) outcomes in the same target group.

The aim of the secondary analyses described in this appendix is to compare infants in 6 different intervention groups: dietary supplementation from age 6 to 18 months with 10 g, 20 g or 40 g per day milk-containing LNS, or 20 g or 40 g per day milk-free LNS, or nothing (delayed intervention) on the following outcomes:

- 1. 18-month motor development, language development, socio-emotional development, executive function, and interaction with caregivers
- 2. Prevalence of severe and moderate to severe delay in motor development, language development, socio-emotional development, and executive function

2. Hypotheses to be tested

- 1. 18-month scores in gross and fine motor development, language development, socioemotional development, executive function, and interaction with caregivers of infants provided with 10, 20, or 40 g/day of LNS from 6 to 18 months of age will be greater than that of infants who receive no dietary intervention at the same age.
- 2. 18-month scores in gross and fine motor development, language development, socioemotional development, executive function, and interaction with caregivers of infants receiving 20 or 40 g/day of LNS without milk from 6 to 18 months of age will not be lower than that of infants receiving a comparable intervention with milk-containing LNS.
- 3. 18-month scores in gross and fine motor development, language development, socioemotional development, executive function, and interaction with caregivers of infants provided with 20 or 40 g/day of LNS from 6 to 18 months of age will be greater than that of infants who receive 10g/day and that of infants provided with 40 g/day will be greater than that of infant who receive 20 g/day.

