5.2 Comparison of milk-containing and milk-free LNS

We will use a two-factor ANOVA/ANCOVA with main effects of dose of LNS (0g, 10g, 20g, or 40g) and milk (yes or no) and the dose by milk interaction. The control and 10g LNS groups will be treated as containing milk. This means that the main effect of milk and the dose by milk interaction are calculated in the model using the data from the 20g and 40g groups only.

If the dose by milk interaction is not significant at the level of p < 0.1, we will conclude that the effect of milk does not differ between the 20g and 40g groups. In this case, the difference in mean scores between the milk-containing and milk-free LNS will be presented as shown in Table 2. A 90% CI will be created for the milk effect, which will be the average of the individual milk effects for the 20g and 40g groups. The set non-inferiority margin for this analysis will be 0.2 Z-score units. If the lower bound of the 90% CI of the coefficient is larger than -0.2, non-inferiority is confirmed. If

the upper and lower bounds of the 90% CI are larger and smaller, respectively, than -0.2, the finding is not conclusive.

If the dose by milk interaction is significant at the level of p < 0.1, we will examine the effect of milk separately in the 20g and 40g groups. In this case, the difference in mean scores between the milk-containing and milk-free LNS will be presented in an expanded version of Table 2 which will present the coefficient, 90% confidence interval, and p-value for (1) the difference in scores in 20g/day LNS with milk versus 20g/day LNS without milk, (2) the difference in scores in 40g/day LNS with milk versus 40 g/day LNS without milk 40g, and (3) the dose by milk interaction term. In this case, a 90% CI will be created for each of the individual milk effects for the 20g and 40g groups. The set non-inferiority margin for this analysis will be 0.2 Z-score units. If the lower bound of the 90% CI of the coefficient is larger than -0.2, non-inferiority is confirmed. If the upper bound of the 90% CI are larger and smaller, respectively, than -0.2, the finding is not conclusive.

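### Appendix 02 section 5.3, second branch: pooling milk and milk-free LNS at 20 g and 40 g against a milk-only 10 g arm adds half the milk effect to the dose comparison

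*SAP*

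**What the plan says.** All references are to SAP Appendix 02 (developmental outcomes).

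- **Arms (section 1).** The active arms are "10 g, 20 g or 40 g per day milk-containing LNS, or 20 g or 40 g per day milk-free LNS". There is no milk-free 10 g arm.
- **Hypothesis 3 (section 2).** Scores with 20 or 40 g/day "will be greater than that of infants who receive 10g/day", and 40 g/day will exceed 20 g/day.
- **Milk comparison (section 5.2).** When the interaction is not significant, the milk effect is "the average of the individual milk effects for the 20g and 40g groups". On how much worse milk-free may be, the plan states: "The set non-inferiority margin for this analysis will be 0.2 Z-score units". Its decision rule reads: "If the lower bound of the 90% CI of the coefficient is larger than -0.2, non-inferiority is confirmed". No upper limit and no equivalence test is set.
- **Dose comparison (section 5.3), second branch.** Its entry condition begins "If the dose by milk interaction is not significant at the level of p < 0.1 and if we conclude that LNS without milk" and ends with a favourable non-inferiority verdict. The branch then applies Scheffe's test in the one-factor model to "the combined 40g group (with and without milk), the combined 20g group (with and without milk), the 10g group, and the control group", and a significant contrast rejects the null hypothesis that higher doses add nothing over lower ones.
- **Dose comparison, third branch.** If non-inferiority is not concluded, dose is taken from the two-factor model of section 5.2 with Tukey-Kramer. The plan says of it: "This model calculates the effect of dose while controlling for the effect of milk".

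**The concern.** The second branch compares groups that are half milk-free with a group that is all milk. That is harmless only if milk has no effect on the score, and neither entry condition shows this. A non-significant interaction says that the milk effect looks similar at 20 g and 40 g, not that it is absent. Non-inferiority rules out a large milk-free deficit but allows an advantage of any size, including one whose own 90% CI excludes zero.

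The third branch already controls for milk. The second drops that control on a one-sided verdict. At stake are the first two comparisons in hypothesis 3, 20 v 10 g and 40 v 10 g, where a formulation effect could be reported as a dose effect.

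**Working it through.** The plan states no bias, power or sample-size figure for this comparison, so there is none to reproduce.

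**Inputs.** 1932 infants in six groups (SAP section 2), assumed equal: n = 1932/6 = 322 per arm, no attrition. SD = 1, since scores are standardised in the sample (Appendix 02 section 6.2). Margin -0.2; Scheffe at adjusted p < 0.05.

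**Bias.** Let d be the milk-free minus milk mean, equal at 20 g and 40 g.

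- Pooled 20 g minus 10 g = (20 g milk - 10 g milk) + d/2. The same holds for 40 g.
- Pooled 40 g minus pooled 20 g: d/2 appears on both sides and cancels.

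**Standard errors.**

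- Milk effect: sqrt(1/n) = 0.0557.
- Pooled 20 v 10 g: sqrt(1/(2n) + 1/n) = sqrt(1.5/n) = 0.068.
- Additive dose + milk model: this subtracts half the estimated milk effect, which adds (1/4)(1/n), so sqrt(1.75/n) = 0.074. Ratio sqrt(1.75/1.5) = 1.08.
- Milk-containing arms only: sqrt(2/n) = 0.079.

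**Entry to the branch.** The lowest milk effect estimate that passes is -0.2 + 1.645 x 0.0557 = -0.108. Half of this is -0.054. Simulated entry (400,000 trials per setting) is 88% at d = 0, 90% at d = +0.1 to +0.4, 50% at d = -0.1 and 4.5% at d = -0.2. At d = +0.2, the 90% CI for the milk effect excludes zero in 97% of the trials that pool.

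**False dose findings with no true dose effect.** The Scheffe limit is sqrt(5 x F(0.95; 5, 1926)) = 3.33. For one contrast the chance of being declared better is P(Z > 3.33 - (d/2)/0.0683). For either of the two correlated contrasts it lies between this value and twice it.

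| d | Bias d/2 | Bias in SE | One contrast | 20 or 40 g better than 10 g (simulated, given pooling) |
|---|---|---|---|---|
| 0 | 0 | 0 | 0.04% | about 0.1% |
| +0.1 | 0.05 | 0.73 | 0.5% | about 0.8% |
| +0.2 | 0.10 | 1.46 | 3.1% | about 5% |
| +0.3 | 0.15 | 2.20 | 13% | about 20% |

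With 225 analysed per arm, the last two simulated figures become about 3% and 11%. With the additive model under the same Scheffe limit, the chance is about 0.1% throughout.

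**Power at a dose effect of 0.2 Z, given entry to the branch.**

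| Analysis | d = 0 | d = -0.1 |
|---|---|---|
| Pooled, Scheffe (as planned) | 47% | 20% |
| Additive, Scheffe | 36% | 26% |
| Milk arms only, Scheffe | 31% | 21% |
| Additive, Tukey-Kramer for 4 dose levels (limit 2.57) | about 67% | - |

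**The case against.** The case for leaving the branch alone has real weight.

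- **Scheffe is conservative.** A reader might infer that pooling inflates false dose findings generally. It does not: up to d = +0.2 the rate is about 5% or less. It clearly exceeds 5% only when milk-free is better by about 0.3 Z, and nothing in the SAP suggests an advantage of that size. Hypothesis 2 expects only that milk-free is not lower. This stands for the test; the estimate is still off by 0.10 Z at d = +0.2, half the plan's margin.
- **The unfavourable side is bounded.** A reader might infer from the margin that a milk-free deficit of 0.2 Z routinely enters and biases the dose contrast by 0.10 Z. At a true deficit of that size, only 4.5% of trials enter. The estimated milk effect must exceed about -0.108, so the estimated distortion is about 0.05 Z, under one standard error.
- **Power.** A reader might set the planned analysis at d = 0 beside the same analysis at d = -0.1 and conclude that pooling costs more than half the power. That compares two milk effects, not two analyses. Like for like at d = -0.1 under Scheffe, it is 20% pooled against 26% adjusted.
- **Pooling is more precise if the formulations are alike.** Under Scheffe at d = 0, adjusting lowers power from 47% to 36%. This is true, but it arises only if Scheffe is kept; the third branch's own Tukey-Kramer test gives about 67%.
- **Visibility and scope.** Table 1 shows all six arms and Table 2 the milk effect with its 90% CI, so a large milk effect would be seen beside the dose result. The comparisons with control in section 5.1 and the primary LAZ analysis do not use this rule. This limits the harm but does not correct the contrast.

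**Conclusion.** The point holds for 20 v 10 g and 40 v 10 g in the second branch, and not for 40 v 20 g. The bias is half the milk effect: +0.10 Z at a milk-free advantage of 0.2 Z and +0.15 Z at 0.3 Z. The false-positive chance at those values is about 5% and 20%, against about 0.1% with no milk effect. It matters mainly if milk-free LNS is better, because the gate leaves that side open.

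These figures assume equal arms of 322, SD 1, no attrition and the same milk effect at both doses. They apply to z-scores where higher is better. The socio-emotional score is lower-is-better (section 3) and the text does not reverse its sign, so for that score the -0.2 limit does not guard against a worse milk-free result and the 0.05 Z bound does not apply.

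This is an inconsistency between two branches of a secondary-outcome analysis, worth correcting because the plan already contains the remedy.

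**What to change.** Merge the second and third branches of section 5.3. Whenever the interaction is not significant, whatever the non-inferiority verdict, take the dose comparisons from the two-factor dose + milk model. State that the interaction term is omitted, and use the Tukey-Kramer adjustment that the third branch already names. Keep the pooled 20 g and 40 g means as description.

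Using the model whatever the verdict also removes a small residue that comes from selecting on non-inferiority: -0.02 Z at d = -0.1 if the adjusted model were used only after that verdict.

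**Cost.** A change of SAP wording and no new data. The standard error of 20 v 10 g and 40 v 10 g rises from 0.068 to 0.074, about 8%. Replacing Scheffe by Tukey-Kramer more than recovers the power (about 67% against 47% at a dose effect of 0.2 Z and no milk effect). The lower limit of 2.57 still keeps the chance of declaring 20 or 40 g better than 10 g, with no dose effect, to at most 2 x P(Z > 2.57) = 2 x 0.005, about 1%.

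Comparing only the milk-containing arms would also remove the bias, but it has the largest standard error (0.079) and recovers little power (21% against 20% at d = -0.1 under Scheffe), so it is not the preferred repair.

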The iLiNS-DOSE trial was designed to study the impact of a 12-month LNS provision to infants and young children on their growth, nutritional status and a number of other health outcomes. For this purpose, a total of 1932 infants were enrolled in rural Malawi, randomized to receive for 12 months either no supplement or one of five alternative LNS-preparations (six study groups in total), and intensely monitored for 12-months for a large number of outcomes. Key details of the trial have been recorded at the clinical trial registry at the National Institutes of Health (USA) (www.clinicaltrials.gov), under the registration number NCT00945698. A full trial protocol is available from the contact person to this document.

This document (called "the statistical analysis plan" or SAP) describes the study group's plan for data analysis, management, and storage. The SAP is designed to be evolving over time. Version 1.0 documents the details of the hypothesis testing and other analyses on primary and selected secondary outcomes. Subsequent versions of the SAP will give further details on the analyses and hypothesis testing of additional secondary outcome variables and exploratory analyses from the data.

3 Study objectives

The main aim of the trial is to assess the safety and impact of LNS supplementation on linear growth of infants and young children and to identify individual, household, and village-level characteristics that would modify the effects of LNS on child growth. A secondary aim is to similarly study the impact of LNS on various other (secondary) outcomes in the same target group. Finally, the trial aims to provide descriptive information on issues that might be necessary to facilitate future demand creation for LNS interventions.

The above aims have been broken down into the following first five objectives that were predefined in the trial protocol. The safety aim was not explicitly stated among the predefined objectives in the trial protocol, but was listed under the primary outcomes for analysis.

- 1. To determine the lowest daily dose of LNS that will promote linear growth among 6-18 months old infants in a rural Malawian community with poor food security. *This covers also the objective to study if ANY dose of LNS promotes linear growth among the target group.*

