Interaction with caregivers is calculated as the sum of the activities with adults in the past three days (*Form 25d Q 4.1.1* through Q 4.5.3).

4. Basis for the analysis: Intention to treat and per protocol

The basis for the analysis will be the same as that for the primary outcomes.

5. Presentation of the study findings and hypothesis testing

5.1 Comparison of the developmental scores at 18 months of age between intervention groups versus the control group

The group means and standard deviations for the gross motor score, fine motor score, psychomotor score, vocabulary score, socio-emotional score, and A not B task total number correct, total errors after set 1, and total trials completed, and the interaction with caregivers score will be presented as indicated in Table 1. Both raw scores and z-scores will be presented. The results of pairwise comparisons will be indicated by superscripts. Means that are significantly different from each other will be marked by different letters (e.g., a and b). Means that are not significantly different from each other will be marked by the same letter.

We will use a one-factor analysis of variance (ANOVA) (or ANCOVA in analyses that include covariates, as specified in section 6.6) to test for differences between the six groups. If the group effect is significant at the level of p < .07, we will use Tukey-Kramer's test for post-hoc pairwise comparisons between each intervention group and the control group. The null-hypothesis of LNS having no impact on development will be rejected for each comparison that yields a Tukey-Kramer's adjusted p-value < 0.05.

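### Appendix 02 section 5.3: as written, one branch of the dose analysis cannot estimate 20 vs 10 g or 40 vs 10 g averaged over milk, and another uses a needlessly wide Scheffé limit

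*SAP*

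**What the plan says.** Hypothesis 3 in Appendix 02 section 2 makes three dose statements. Scores in children "provided with 20 or 40 g/day of LNS from 6 to 18 months of age will be greater than that of infants who receive 10g/day" (20 vs 10 and 40 vs 10), and scores of "infants provided with 40 g/day will be greater than that of infant who receive 20 g/day" (40 vs 20).

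Section 5.1 fits a one-factor model "to test for differences between the six groups". Section 5.2 fits a two-factor model with "main effects of dose of LNS (0g, 10g, 20g, or 40g) and milk (yes or no) and the dose by milk interaction". On coding it says: "The control and 10g LNS groups will be treated as containing milk".

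Section 5.3 then has three branches:

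1. Interaction significant (p < 0.1): Tukey-Kramer in the six-group model.
2. Interaction not significant and milk-free LNS judged non-inferior: "we will use Scheffe test in the one-factor ANOVA/ANCOVA described in section 5.1 to compare the mean scores among the combined 40g group", the combined 20 g group, the 10 g group and control.
3. Interaction not significant and non-inferiority not concluded: "we will use Tukey-Kramer's test for post-hoc pairwise comparisons between each intervention group in the two-factor ANOVA/ANCOVA described in section 5.2". The next sentence says that this model gives a dose effect adjusted for milk.

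Section 5.4 applies the same approach to the logistic models for developmental delay. Section 6.3 names Tukey-Kramer as the adjustment and does not mention Scheffé.

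**The concern.** In branch 3 the model and the comparison do not fit together. Four dose levels crossed with milk yes/no make eight cells, of which only six were randomised. With the interaction in the model, a dose mean averaged over milk needs both milk cells at that dose, and at 0 g and 10 g one of them is empty. The analyst would have to settle on a different model after seeing the interaction and non-inferiority results.

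In branch 2 the comparisons are known in advance: four dose means and six pairs. Scheffé protects against every possible contrast among six groups, so the trial pays for protection that it does not plan to use. Branch 2 is the usual route if milk has no effect, so the loss of power falls on the most likely form of the dose analysis.

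**Working it through.** The appendix gives no sample size, power or critical value, so there is no figure of its own to reproduce.

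**Branch 3: estimability**

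Write each cell mean as μ(d,m) = μ + α_d + β_m + γ_dm. The observed cells are 0 g, 10 g, 20 g and 40 g with milk, and 20 g and 40 g without. The milk-averaged dose mean is M_d = ½[μ(d,yes) + μ(d,no)].

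- M_20 − M_10 and M_40 − M_10 both contain μ(10,no), and hence γ(10,no), which appears in no observed cell. They are not estimable.
- M_40 − M_20 uses four observed cells. It is estimable.
- A rank check agrees. With the interaction the design has rank 6, and every milk-averaged difference involving 0 g or 10 g fails; 40 vs 20 g passes. Without the interaction the rank is 5, and all six differences pass, because M_20 − M_10 reduces to α_20 − α_10.
- Standard errors in the additive model, with SD 1 and n = 322 per arm: √(1.75/322) = 0.0737 for 20 vs 10 and 40 vs 10; √(1/322) = 0.0557 for 40 vs 20.

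**How often branch 3 arises**

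The SE of the averaged milk effect is √(1/n) on the z-score scale. With margin 0.2 and a 90% CI, the chance that non-inferiority is not shown at true milk effect δ is Φ((−0.2 − δ)/SE + 1.645).

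| n per arm | δ = 0 | δ = −0.05 | δ = −0.10 |
|---|---|---|---|
| 260 (assumed) | 6% | 22% | 51% |
| 322 (upper limit) | 2.6% | 15% | 44% |

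The branch also needs a non-significant interaction, about 90% likely if there is none. It is therefore reached in about 5%, 20% and 46% of cases at n = 260, and 2%, 13% and 40% at n = 322.

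**Branch 2: critical values on the t scale**

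The main SAP says "a total of 1932 infants were enrolled in rural Malawi". That is 1932/6 = 322 per arm and 1926 error df, if allocation was equal and follow-up complete. The value of 260 is an assumption that allows for losses. Alpha is 0.05, taken as two-sided.

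- Scheffé, six groups: √(5 × F(0.95; 5, 1926)) = 3.331
- Bonferroni, six pairs: t(1 − 0.05/12) = 2.641, so Scheffé is 3.331/2.641 − 1 = 26% wider
- Tukey on four means: 2.571 (Scheffé 30% wider)
- Tukey on six means: 2.853 (17% wider)
- Bonferroni on the three LNS-dose pairs only: 2.396 (39% wider)
- Scheffé confined to the 3 df of the four pooled means would be 2.798, only 6% above Bonferroni for six pairs

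The ratios do not change at 1494 error df.

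**Branch 2: power**

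Power ≈ Φ(0.2/SE − c) with SD 1. SE is √(1/n) for combined 40 vs combined 20 g, and √(1.5/n) for combined 20 vs 10 g.

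| Contrast | n per arm | 0.2/SE | Scheffé | Bonferroni |
|---|---|---|---|---|
| 40 vs 20 g | 260 | 3.22 | 0.46 | 0.72 |
| 40 vs 20 g | 322 | 3.59 | 0.60 | 0.83 |
| 20 vs 10 g | 260 | 2.63 | 0.24 | 0.50 |
| 20 vs 10 g | 322 | 2.93 | 0.34 | 0.61 |

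At n = 322, Scheffé against Bonferroni gives 0.26 vs 0.52 (40 vs 20 g) and 0.13 vs 0.33 (20 vs 10 g) for a 0.15 SD difference, and 0.88 vs 0.97 and 0.63 vs 0.85 for 0.25 SD. Holm rejects whenever Bonferroni does, so the Bonferroni figures are a floor for Holm.

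**The case against.** On branch 3, the case is that the wording is loose but the intention is clear. The branch is entered only when the interaction is not significant, and the plan says the model adjusts dose for milk, which describes an additive model in which every dose contrast is estimable. The comparisons could also be read as differences between cell means. Under 0/1 coding the dose coefficients are contrasts among milk-containing arms. Both are estimable.

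The point about intention stands and softens the criticism, but it does not settle the plan. Main SAP section 11.4 says explicitly that a model without the interaction will be fitted; Appendix 02 has no such sentence. The cell-mean reading does not help. Six parameters for six cells is the six-group model of section 5.1, so branch 3 would repeat branch 1 and would not adjust for milk as it says.

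On branch 2, Scheffé controls family-wise error and suits pooled contrasts in a six-group model. That stands: the choice is valid. With larger effects it costs less; at 0.3 SD and 260 per arm, Scheffé power is 0.93 (40 vs 20 g) and 0.73 (20 vs 10 g).

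A reader might infer three stronger claims that the document does not support:

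- *The dose hypothesis is lost in branch 3.* One of its three comparisons survives. The contrasts with control, which are also non-estimable there, belong to hypothesis 1 and are tested in section 5.1.
- *Scheffé is an error.* It is an efficiency loss.
- *Non-rejection will be reported as no dose effect.* Section 5.3 gives only a rejection rule.

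**Conclusion.** The point holds in two limited parts. The estimability result rests only on the model as written and needs no numerical assumption: branch 3 cannot supply the milk-averaged 20 vs 10 g and 40 vs 10 g differences, and 40 vs 20 g remains. If milk has no effect the branch is uncommon (about 2 to 5% of scores); it is frequent if milk-free LNS is slightly worse (about 40 to 46% at −0.10 SD).

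In branch 2 the Scheffé limit is about 26% wider than Bonferroni for the six named contrasts. The excess runs from about 6% to 39%, depending on the comparator and on the Scheffé df; 5 df follows from the six-group model that the plan cites. The loss of roughly 23 to 27 percentage points of power assumes a 0.2 SD difference, unit SD, equal arms of 260 to 322 children and no covariate gain. These are secondary outcomes, and the plan should be corrected because the change is small.

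**What to change.** - In section 5.3, branch 3, state that the model is refitted with dose and milk main effects and without the interaction, following main SAP section 11.4. All six dose contrasts are then estimable.
- In branch 2, keep the six-group model, write out the six contrasts among control, 10 g, combined 20 g and combined 40 g, and adjust them by Holm, which the main SAP already uses for efficacy.
- Carry both changes into the logistic models of section 5.4.
- Amend section 6.3 so that it names the adjustment used in each branch.

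The cost is a few sentences and a few lines of code. The one thing given up is simultaneous coverage of contrasts outside the six, and none is planned in that branch.
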